8.1. Sample Size/Power Calculation

The objective of the power analysis was to determine the minimum sample size needed to reject the null hypothesis that the three-way genetic information by health coaching by time interaction was equal to zero in the context of a longitudinal general linear mixed model. The model was assumed to have two levels of genetic information (present or absent), two levels of health coaching (present or absent), and five levels of time (0, 1.5, 3, 6 and 12 months after randomization). In producing the required sample-size estimates, we further assumed that each of the four group means over time would take on standardized mean values. The type I error rate was set to be no greater than .025 as there will be two primary analyses. Controlling each one at no greater than .025 controls the overall experiment type I error rate to be no greater than .05. Calculations indicated that with a sample size of 99 subjects per group, or 396 total, the power to reject the null hypothesis concerning the three-way interaction was .80. Assuming an attrition rate of at most 15% and the current pilot diabetes study attrition of 11%, over the 12 month time period we calculated a possible required sample size of $(396/.86)=460$ to attain the target sample of 400. Sample size calculations are not provided for detecting the direct effects or interactive effects of the two interventions pooled over time, primarily because we expect the genetic information by health coaching interaction to change over time, as reflected in the three-way interaction.

Due to delayed/slow recruitment the sample size is revised as following (modification approved in contract amendment):

A reduced sample size, but collecting data out to 12 months as planned:

- a. Coming from the stance that we want to preserve as much of the original thinking behind the power analysis as possible, we eliminated the calculation and testing of the three way

interaction which was originally planned. This three way interaction said that the interaction of Health Coaching and genetic testing peaks at 6 months. The idea was that there was a synergy between genetic testing and health coaching which would push health behavior means for the subjects receiving both components to far greater than the individual effects of either one. Elimination of the three way interaction takes away our ability to say when this occurs (time).

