Pattern	Type I error rate	Power	Within Person Correlation	Sample Size per Group	Total Sample Size
1	.025	.80	.350	25	100
1	.025	.85	.350	27	108
2	.025	.80	.350	44	176
2	.025	.85	.350	49	196
3	.025	.80	.350	56	224
3	.025	.85	.350	63	252

- b. Means for the four groups pooled across time showing JUST the coaching by genetics testing interaction for each pattern.
- c. Examining the health coaching by time and the genetic testing by time interactions. Assuming the same means over time for pattern 2, the means for the two interactions would be as shown in the two tables immediately below.

Health coaching by time interaction for pattern 2

	NO HC	HC
0	0.05	0.05
1.2	0.15	0.5
3	0.275	0.95
6	0.125	1.5
12	0.05	0.85

Genetic testing by time interaction for pattern 2

	No Genetics	Genetics
0	0.05	0.05
1.2	0.225	0.425
3	0.425	0.8

6	0.525	1.1
12	0.225	0.675

d. Results of power calculations when the three way interaction for the groups, as well as the three way interaction for time by health coaching by genetic testing are eliminated. These are the power for detecting the interaction which is the smallest (the genetic testing one).

Pattern	Type I error rate	Power	Within Person Correlation	Sample Size per Group	Total Sample Size
2	.025	.80	.350	43	172
2	.025	.85	.350	49	196

While we will have lost the power to examine a 3-way interaction (health coaching by genetic risk testing by time), with the participants, we will still be able to:

- 1) Examine 2 way interaction effects of health coaching by time and genetic risk testing by time (estimated minimum sample needed 172-196);
AND/OR
- 2) Examine the 2 way interaction of health coaching and genetic risk testing (comparative effectiveness without time point considered in interaction; estimated sample needed 176-196).

Assuming an attrition rate of at most 15% the required minimum sample size is 212.

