8.2. Analysis Plan

Demographic characteristics of the sample (income level, age, gender, race/ethnicity, educational level) will be provided using descriptive statistics to describe the overall sample and by group to ensure that randomization was effective. Distribution of variables will be determined prior to further statistical analysis. SAS software (80) will be used for all analyses.

To address the primary aims, mixed models will be used. The first aim is to determine the direct and interactive effects of genetic risk information incorporated with standard CHD/T2D risk counseling and a health coaching intervention for CHD/T2D on behavior change (diet, physical activity) in AF primary care patients over 12 months. The goals of the statistical analysis will be to quantify: (1) the extent to which genetic risk counseling influences the trajectory of change in physical activity and diet measures from baseline to 3, 6, and 12 months; and (2) the extent to which the genetic risk information augments the trajectory of the effects of health coaching on diet and physical activity measures over the same time period. We will fit two general linear mixed models to these data (81), with

physical activity and diet measures at each of the five points in time. For either model, there will be three independent variables: genetic risk information (G) with values of 1 or 0, health coaching (HC), also with values of 1 or 0, and time since randomization, with values of 0, 3, 6, and 12 months. Within the context of the linear mixed model, we should observe a statistically significant three way interaction of time by genetic information by health coaching. The particular type of longitudinal model selected for analysis will depend upon preliminary analyses of the data. For example, a subject specific (also called hierarchical) model with random intercept and slope assumes that within subject variances increase or decrease over time. A model hypothesizing only a random intercept does not assume that within subject variances show this pattern. Another consideration will be the extent of missing data; some longitudinal models are better than others at handling missing data.

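### Section 8.2 still expects a significant three-way interaction that section 8.1 removed, and no confirmatory two-way test or sharing of each .025 replaces it

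*Combined protocol and SAP*

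**What the plan says.** **Section 8.1, error rate.** The plan states: "The type I error rate was set to be no greater than .025 as there will be two primary analyses". It adds: "Controlling each one at no greater than .025 controls the overall experiment type I error rate to be no greater than .05". It does not say which two analyses are meant.

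**Section 8.1, revision after slow recruitment.** Of the genetics-by-coaching-by-time interaction the revision says "we eliminated the calculation and testing of the three way", and it later concedes that power for this term is lost. Two options are kept, joined by an and/or: "Examine 2 way interaction effects of health coaching by time and genetic risk testing by time", and "Examine the 2 way interaction of health coaching and genetic risk testing (comparative effectiveness without time point considered in interaction". The section closes with "Assuming an attrition rate of at most 15% the required minimum sample size is 212". Section 5.1 plans 250 enrolled.

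**Section 8.2.** The text on the primary mixed models still says that "we should observe a statistically significant three way interaction of time by genetic information by health coaching". This is the only significance result named for those models. Two mixed models are described, for physical activity and diet. A second part of the primary analysis then applies the same analysis to seven metabolic outcomes: fasting glucose, SBP, BMI, waist, LDL, triglycerides and total cholesterol.

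**The concern.** Section 8 gives two answers on whether the three-way term is tested. The clash is between the revised part of 8.1 and the current 8.2. It does not depend on the superseded 396/460 calculation.

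Removing the term also leaves a gap. Goal (1) of 8.2 corresponds to genetics-by-time, but it is worded as quantification. None of the three retained two-way tests is called confirmatory, and no order is given. The two primary analyses could be activity and diet, or behavioural and metabolic. On the first reading the metabolic outcomes have no alpha. On the second, one .025 covers two outcomes and the other covers seven.

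The test that carries the conclusion could therefore be chosen after the data are seen, and the stated overall .05 is unsupported. A null three-way result at the reduced size could also be misread as evidence against synergy.

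**Working it through.** **1. The plan's own error figure.** 2 × .025 = .05 (1 − .975² = .049 if independent). It reproduces, but only with one test per primary analysis.

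**2. Error bounds if nothing is shared.**
- Diet and activity, three two-way tests each: 3 × 2 × .025 = 0.15 (1 − .975⁶ = 0.141 if independent).
- Behavioural (2 outcomes) and metabolic (7), one test per outcome: 9 × .025 = 0.225 (1 − .975⁹ = 0.204 if independent).

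**3. Sample sizes.** 250 × .85 = 212.5, so about 212 analysed. Reading the minimum of 212 as enrolled, 212 × .85 = 180.2, so about 180 analysed.

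**4. Method for power.** Solve the noncentrality λ from a size and power stated in 8.1 at alpha .025, then scale it by N. For 1 df, λ = (2.241 + 0.842)² = 9.505, and power at .025 is Φ(√λ′ − 2.241), where λ′ is the scaled value. For 4 df (five time levels), λ = 14.06. Tabulated powers use the noncentral F; the chi-square version agrees within .005.

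**5. Three-way term**, scaled from 396 at power .80:
- 4 df: 14.06 × 212/396 = 7.53, power 0.46; 14.06 × 180/396 = 6.39, power 0.39.
- 1 df: 9.505 × 212/396 = 5.09, power 0.51; 9.505 × 180/396 = 4.32, power 0.435.

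**6. Coaching-by-genetics** (1 df), scaled from 176 (pattern 2) and 224 (pattern 3). Example, pattern 2 at 212: λ′ = 9.505 × 212/176 = 11.45, and Φ(3.384 − 2.241) = 0.873.

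| Pattern | Analysed | Power at .025 | Power at .0125 |
|---|---|---|---|
| 2 | 212 | 0.874 | 0.812 |
| 2 | 180 | 0.810 | 0.731 |
| 3 | 212 | 0.775 | 0.690 |
| 3 | 180 | 0.698 | 0.602 |

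Pattern 3 needs 224 analysed for .80, which is 224/.85 = 263.5, about 264 enrolled. The 176 to 196 given in 8.1's closing list is pattern 2 only.

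**7. Genetics-by-time, pattern 2**, by two routes.
- *Scaled from 172* (3 to 4 df).
- *From the printed means.* The genetics-minus-none differences are 0, .20, .375, .575 and .45. Assume SD 1 and compound symmetry with the stated correlation of .35. Then λ = N × SS/(4 × .65), where SS is the sum of squared deviations of the differences from their mean: 0.202 with five times, 0.184 with four. At N = 172 and five times, λ = 13.35 and power is 0.77, a little below the stated .80. An SD of .97 closes the gap, so this route is slightly pessimistic and does not show an error in 8.1.

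| Analysed | Route | Power at .025 | Power at .0125 |
|---|---|---|---|
| 212 | scaled | 0.890–0.892 | 0.835–0.838 |
| 212 | means | 0.863–0.868 | 0.800–0.807 |
| 180 | scaled | 0.822 | 0.748–0.749 |
| 180 | means | 0.789–0.793 | 0.709–0.714 |

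**8. Coaching-by-time, pattern 2.** From the printed means, power exceeds 0.99 at 180 analysed, even at .025/3 = .0083.

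**The case against.** The strongest reply is that 8.1 presents itself as the approved revision and admits the lost power, so a reader can tell that the sentence in 8.2 is stale. Section 5 also calls the primary outcomes behavioural. With the two mixed models of 8.2, this favours diet and activity, and then .05 can hold.

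Part of this stands. The three-way sentence alone would be an editing matter, and the two analyses are better described as ambiguous between two readings than as wholly unspecified. But section 2 lists clinical outcomes under its primary aims, Table 2 has a primary clinical heading, and 8.2 calls the metabolic outcomes part of the primary analysis. Even on the diet-and-activity reading, the and/or leaves up to three tests per outcome.

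Some limits on the figures are fair:
- The error bounds are ceilings, and correlated outcomes would put the actual rate lower. The two bounds also use different numbers of tests per outcome; three tests on nine outcomes would give 27 × .025 = 0.675.
- That 212 is a pre-attrition figure is the natural reading (180/.85 = 211.8), but no tabulated size leads to it exactly: 172/.85 = 202.4 and 176/.85 = 207.1.
- Mixed models can use partial follow-up, so counting attrition as full loss is conservative, although 8.1 does the same.

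None of these removes the contradiction or supplies the missing rule.

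**Conclusion.** The concern holds and must be fixed. Current text both eliminates the three-way test and expects it to be significant, and the overall .05 is secured only under a reading the plan never adopts: diet and activity as the two analyses, one confirmatory test each, and metabolic outcomes not confirmatory.

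The contradiction and the missing alpha rule follow from the text alone. The power figures rest on 8.1's behavioural planning effects and on 15% attrition as complete loss. The printed-means figures also need SD 1 and compound symmetry, which the plan does not state. On that basis the three-way test has roughly an even chance of detecting the original planning effect at 212 analysed, and less at 180. The two-way tests are adequately powered under pattern 2 at 212 analysed, while coaching-by-genetics under pattern 3 misses .80 at both sizes.

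**What to change.** 1. In 8.2, delete the expectation of a significant three-way interaction. Report any three-way estimate as exploratory with a confidence interval, including goal (2) if it is kept as trajectory estimation.
2. In 8.1 and 8.2, define the two primary analyses and say whether the metabolic outcomes are confirmatory.
3. Replace the and/or with the named confirmatory two-way test or tests, and state a fixed order or a division of each .025 across tests and outcomes.
4. State power at the resulting alpha, by pattern, for 250 enrolled (about 212 analysed) and for 212 enrolled (about 180 analysed).
5. Correct the leftover n=200 for the two coaching arms (5.3.2) and the two genetic arms (8.2). Two of four arms are about 250/2 = 125, or 212/2 = 106, before attrition.

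**Cost.** Text changes only, with no new data or visits. The trial gives up a confirmatory claim about when synergy occurs, which 8.1 already concedes. Splitting .025 over two tests costs about 5 to 6 points of power at 212 analysed and 7 to 8 at 180, for genetics-by-time and coaching-by-genetics under pattern 2. At 180 these then stand at 0.71 to 0.75. Under pattern 3 the cost for coaching-by-genetics is about 8 to 9 points at 212 and 9 to 10 at 180. A fixed order costs the first test nothing but makes later tests depend on it.

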Additional biweekly calls. HC calls then follow the general template of the coaching prep form. All HC sessions begin with a brief check-in, reporting on specific action steps from the preceding week(s). Participants are trained to note success first, then to problem-solve and explore solutions for upcoming obstacles. Importantly, they learn from failed problem-solving attempts, which are non-judgmentally framed as “experiments” necessary for true learning. Non-judgmental framing is essential to maintaining rapport and encouraging clients to experiment with solutions without fear of failure. Participants then commit to new action steps toward their goals to be accomplished before the next call, and clarify what resources they will need to accomplish them. Of note, the health coaches will be blinded to the participants’ genetic risk results; however, participants may choose to disclose them to the coaches, mimicking actual utilization of this information (Appendix D.).

Table 2. Study Measures	Baseline	6 wks	3 mos	6 mos	12 mos
Eligibility Screen & Informed Consent	X				
Demographic Questionnaire	X				
Family history of CHD & T2D	X				
Blood collection for genetic testing	X				
Primary Outcomes: Behavioral					
Wheel of Health	X	X		X	
Dietary Intake (NCI Multifactor Screener)	X		X	X	X
Physical Activity (SBAS)/Wellness Programs	X		X	X	X
Smoking Status	X		X	X	X
Medication Adherence (Morisky 4)	X	X		X	X
Primary Outcomes: Clinical					
Height for BMI calculation	X				
Weight	X			X	X
Waist Circumference	X			X	X
Blood pressure	X			X	X
Medications	X			X	X
Lab tests (fasting glucose, total cholesterol, HDL, LDL, triglycerides)	X				X
Fitness Status (Air Force Fitness Score)	X				X
Risk Status (FRS and T2D Risk Score)	X				X
Adverse Events Assessed				X	X
Potential Mediators					
Perceived Risk for CHD & T2D	X	X		X	
Worry, Self-efficacy	X	X		X	
Patient Activation	X	X	X	X	X
Stages of Change	X	X	X	X	
Psychosocial Risk Factors: Depression (BDI), stress level (PSS) social isolation (social support item) Hostility (cook-medley)	X X			X	

6. Adverse Events

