The second part of the primary analysis will determine the direct and interactive effects of genetic risk information incorporated with standard CHD/T2D risk counseling and a health coaching intervention for CHD/T2D on metabolic outcomes (fasting blood glucose, SBP, BMI, waist circumference, LDL, triglycerides, total cholesterol) over 12 months. The statistical analysis will be the same as above except that the dependent variables will be fasting blood glucose, SBP, BMI, waist circumference, LDL, triglycerides, and total cholesterol.

To address Aim 2, we will examine the mediating effects of level of CHD/T2D genetic risk (number of risk alleles) and consequent reclassification of FRS in the case of CHD risk (decreased, neutral, or increased) on behavior change (diet, physical activity) at 6 months. The goal of this analysis is to quantify the extent to which subgroups of patients exhibit different levels of change in diet and physical activity behavior at 6 months post randomization depending on reclassification of FRS and T2D risk level. We also want to know if the differences depend on whether or not the genetic results were delivered in the context of health coaching. For these analyses, we will use results from only the two groups of patients randomized to receive genetic testing (n=200). Because we will have only two points in time, we will use the simpler linear regression model, with the dependent variable being either diet or physical activity collected at 6 months post randomization. There will be six independent variables: the outcome measured at baseline (a covariate), the results of the genetic testing (entered as two dummy coded variables), a dummy coded variable to indicate the presence or absence of health coaching, and two dummy coded variables representing the interaction of health coaching and the results of genetic testing. We are particularly interested in comparing the diet and physical activity changes of patients whose genetic test results move their Framingham risk or T2D levels either up or down (based on number of higher-risk alleles) to those whose genetic

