Secondary analyses will examine the mediating effects of perceived CHD/T2D risk, self-efficacy, worry, patient activation and readiness for change on the effects of genetic risk information on diet and physical activity at 6 months post randomization. The analytic strategy will be to determine the extent to which genetic risk treatment effects on diet and physical activity occur subsequent to treatment effects on perceived CHD/T2D risk, self-efficacy, worry, patient activation and readiness for change. For example, one set of analyses will estimate the direct relationship between genetic risk counseling and changes in physical activity at 6 months (independent of evaluation of the effects of treatment on perceived risk). Additionally, the extent to which genetic risk counseling influences perceived risk at 6 weeks and 3 months post randomization, *which in turn affects behavior change at 6 months*, will be assessed. This analysis will be repeated using diet as the dependent variable. Then both will be repeated using self-efficacy, worry, patient activation and readiness for change as mediators. In each analysis, mediation will be estimated via a series of linear regressions. Mediation will be *tested statistically* by examining the empirically generated sampling distribution of the parameters involved in the mediational hypothesis: the effect of treatment on the mediators at 6 weeks and 3 months, the effect of the mediators at 3 months on the dependent variable at 6 months, and the product of these effects. We will use bootstrapped sampling distributions of the parameters involved in each mediational hypothesis. Recent work supports this method rather than the more traditional Sobel tests, especially with smaller samples.

9. Protection of Human Subjects

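### The 6-month genetic-result regression is justified by having only two time points, but diet and activity are measured at four. As written it leaves collected data unused, at a small, conditional cost in bias.

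*Combined protocol and SAP*

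**What the plan says.** Section 8.2 (Analysis Plan) restricts this analysis to the two groups that receive genetic testing and asks how behaviour at 6 months relates to the genetic result, with and without coaching. The reason for the model is "Because we will have only two points in time, we will use the simpler linear regression model". Its response is the month-6 value of one behaviour at a time, diet in one fit and activity in another. The predictor list opens "There will be six independent variables: the outcome measured at baseline (a covariate" and continues with two result dummies, a coaching dummy and two interaction terms. No 3-month or 12-month value enters.

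The schedule is wider than that. In Table 2 (section 5.3.2), the row beginning "Dietary Intake (NCI Multifactor Screener" and the row "Physical Activity (SBAS)/Wellness Programs" are both marked at baseline, 3, 6 and 12 months. The primary models in section 8.2 use "time since randomization, with values of 0, 3, 6, and 12 months" for the same two outcomes.

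The only remark on missing data in section 8.2 concerns the choice of the primary longitudinal model: "Another consideration will be the extent of missing data; some longitudinal models are better than others at handling missing data". No rule is given for the 6-month regression.

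**The concern.** The stated reason for leaving the longitudinal model does not describe the data the trial collects. A regression with one outcome per person cannot use a participant who lacks that outcome, unless a missing-data method is added. Someone who reported at 3 months and then missed month 6 contributes nothing, although the 3-month value is in the database.

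The analysis asks whether people told that their genetic risk is higher or lower behave differently afterwards. Suppose those who do poorly after a high-risk result leave more often than those who do poorly after a neutral one. The remaining high-risk participants then look better than the full group, and the contrast is pushed towards an apparent benefit of that result. A model that uses the 3-month value removes this distortion when loss depends on behaviour already observed.

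**Working it through.** **Inputs from the documents.** Within-person correlation .35 and attrition of at most 15% over 12 months (section 8.1). Enrolment of 250 (section 5.1), so 250/2 = 125 tested participants. The 200 given for this regression is half of the superseded target of 400. The pattern 2 genetics table in section 8.1 gives differences of 0 at baseline, .375 at 3 months, .575 at 6 and .45 at 12.

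**Assumptions.** SD 1; equal correlation between all visits; loss logistic in the 3-month value; loss by 6 months of 15%, with 25% as a heavier case. The plan gives no 6-month loss. Section 5.3.1 sets extended analysis windows for 6 weeks, 3 and 12 months but none for 6 months, so heavier loss there is possible. Result categories are taken as equal in size: 125/6, about 21 per result-by-coaching cell.

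**The plan's own figure.** The only current figure that carries the attrition is the minimum of 212. From 176, 176/.85 = 207.1, or 208 in four equal groups, within 2% of 212. The exact figure would need 180/.85 = 211.8. The gap does not affect this point.

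**Participants affected.** .15 × 125 = 18.75, about 19, if the whole 12-month loss has occurred by month 6. Some of these would have left before month 3 and have no 3-month value to use.

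**Precision.** The partial correlation of the 3- and 6-month values given baseline is (.35 - .35²)/(1 - .35²) = .2275/.8775 = .259.
- Month 3 explains .259² = .067 of the remaining variance. At 15% loss the variance falls by .15 × .067 = 1.0%.
- Months 3 and 12 together explain 2 × .0672/1.259 = .107. The fall is .15 × .107 = 1.6%.

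**Standard error.** With the coaching interactions in the model, a result coefficient compares two cells: √(2 × .8775/(21 × .85)) = .31 at 15% loss and √(2 × .8775/(21 × .75)) = .33 at 25%.

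**Bias.** To first order, selection on the 3-month value moves a group's adjusted 6-month mean by slope × loss × .35 × (1 - .35) = slope × loss × .2275, where slope is the log-odds of retention per SD. The contrast is biased only by the difference between the groups' shifts. First-order values are set beside simulated ones:

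| Loss mechanism | Loss | First order | Simulated |
|---|---|---|---|
| Same in both groups, no 3-month difference | 15% | 0 | within .003 |
| Same, 3-month difference .375, slope 1 | 15% | (.171 - .129) × .2275 = .010 | .008 |
| Same, 3-month difference .375, slope 2 | 15% | (.182 - .117) × 2 × .2275 = .030 | .019 |
| One group only, slope 1 to 1.5 | 15% | .034 to .051 | .03 to .05 |
| Opposite directions, slope 1 | 15% | .068 | .06 |
| One group only, slope 1 to 1.5 | 25% | .057 to .085 | .05 to .07 |
| Opposite directions, slope 1 | 25% | .114 | .10 |

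The approximation overstates at steep slopes. In rows two and three the bias shrinks the contrast. The genetics differences compare tested with untested arms and stand in here because the plan gives no effect size by result. Estimates that used the 3-month value stayed within about .006 SD of the truth in every setting. The correlation matters little, because .35 × .65 = .2275 and .5 × .5 = .25 are close.

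**Effect on a test.** At a two-sided 5% level (assumed), a bias of δ standard errors gives an error rate of Φ(-1.96 + δ) + Φ(-1.96 - δ). For .03/.31 = .10 this is 5.1%; for .06/.31 = .19, 5.4%; for .10/.33 = .30, 6.0%.

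**The case against.** The sentence may mean only that this analysis uses two values, baseline and 6 months. The question is set at 6 months, and adjusting the 6-month value for baseline is a standard answer to it. That stands as a defence of the target. It does not rescue the rationale, which offers the number of time points as the reason for leaving a longitudinal model when four exist.

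A reader might infer that the plan prescribes a complete-case analysis. It does not use the term; it is silent on missing data here. Dropping people without a 6-month value is what the written model does unless something is added.

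A reader might also infer that the contrast is biased whenever loss depends on 3-month behaviour. The first row of the table shows that it is not: an equal shift in both groups cancels. Differential loss by result group is plausible, since the analysis exists to study differing reactions to results, but nothing in the documents shows that it will occur. If only half the 12-month loss falls before month 6 (assumed), the one-group bias is about .01-.02 SD.

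It is tempting to extend the point to the mediation analysis, where "mediation will be estimated via a series of linear regressions". The two-time-point reason is not given there, 3-month mediators are already used, and no calculation here supports the extension.

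Finally, carrying the Aim 1 model over unchanged could do harm, because section 8.2 leaves its form open. A straight line through the genetics differences at 0, 3, 6 and 12 months has slope 2.625/78.75 = .0333 about a mean of .35 at 5.25 months. It gives .35 + .75 × .0333 = .375 at month 6 instead of .575. That .20 SD error exceeds every bias in the table. This objection stands and shapes the fix.

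**Conclusion.** The rationale contradicts the plan's own schedule, and the written model leaves usable 3- and 12-month data out. The statistical cost is small and conditional. It is nil when the loss mechanism is common to the groups and they do not differ at 3 months. It is about .01-.02 SD with the plan's genetics differences, and about .03-.06 SD at 15% loss if the mechanism differs by result group. It reaches about .10 SD only with loss acting in opposite directions at an assumed 25%. Against a standard error of .31-.33 SD, that is at most about three tenths of a standard error. The case for change rests on an incorrect premise and an avoidable bias; power hardly moves. These sizes depend on the assumed loss model, equal cell sizes and a common correlation of .35. The point is minor.

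**What to change.** Delete the two-time-point rationale in section 8.2. In the two genetic-testing groups, fit a repeated-measures model to the 3-, 6- and 12-month values with categorical time, result group by coaching by time, baseline by time, and unstructured covariance. From it take the same baseline-adjusted 6-month contrasts, low versus unaffected and high versus unaffected, and their coaching interactions. Multiple imputation of the 6-month outcome using the 3- and 12-month values is an acceptable alternative. State that the analysis assumes data are missing at random given the observed values, and keep the completer regression as a sensitivity analysis. With no missing data the two approaches give the same 6-month estimates, so the target is unchanged.

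The cost is revised wording, slightly more programming, and six covariance parameters (three variances, three covariances) in place of one residual variance. No new data are needed.
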